### 3.5. ADMINISTRATION OF STUDY MEDICATION

Subjects will receive either 15mg APL-2/100 µL IVT injections or sham injections. Injections will either be monthly or EOM depending on the treatment group. The number of injections for each treatment group is:

**Table 1: Number of Injections**

Treatment Arm	Number of Injections
APL-2 Monthly for 12 months	13
APL-2 EOM for 12 months	7
Sham Monthly for 12 months	13
Sham EOM for 12 months	7

## Statistical Analysis Plan

---

APL-2 injections will be administered using a 29G or 27G thin wall needle, at the discretion of the investigator. The procedure for the sham injection will be the same as that used for IVT injection until the actual injection; no actual injection will occur. Detailed instructions on drug preparation, pre-injection procedures, administration of APL-2, sham injections and post-injection procedures are provided in the manual of procedures for this study.

To minimize intra ocular pressure (IOP) elevation after IVT injection of APL-2, decompression of the eye must be performed before all APL-2 (or sham) injections. This is done by applying moderate pressure to the globe with cotton swabs for 30-60 seconds during anaesthetic preparation.

Statistical Analysis Plan

**3.6. STUDY FLOWCHART**

Monthly Groups Visit Schedule																	
Visit #	Screening	Treatment														FU	Termin.
	1	2	3	4	5	6	7	8	9	10	11	12	13	14	15	16	17
Day	-14	0	7	30	60	90	120	150	180	210	240	270	300	330	360	450	540
Deviation Allowed (+ or - days)	5	0	2	6	6	6	6	6	6	6	6	6	6	6	6	14	14
Month	-0.5	0	0	1	2	3	4	5	6	7	8	9	10	11	12	15	18
Informed Consent / Assign Screening Number	x																
Demographic Data	x																
Inclusion/Exclusion Criteria A	x	X															
Medical/Ocular History	x																
Blood Draw – Safety Labs B	x				x				x						x		x
Urine Sample Collection	x				x				x						x		x
Blood Draw - PK and Anti-APL-2 Ab	x		x	x	x	x	x	x	x	x	x	x	x	X	x	x	x
Blood Draw – Genotyping (if applicable) C					x												
Vital Signs D	x	X	x	x	x	x	x	x	x	x	x	x	x	X	x	x	x
Urine Pregnancy Test E				x	x	x	x	x	x	x	x	x	x	X	x	x	x
BCVA	x	SE	SE	SE	SE	SE	SE	SE	SE	SE	SE	SE	SE	SE	SE	x	SE
LL-BCVA	x	SE	SE	SE	SE	SE	SE	SE	SE	SE	SE	SE	SE	SE	SE	x	SE
IOP Measurement	x	SE	SE	SE	SE	SE	SE	SE	SE	SE	SE	SE	SE	SE	SE	SE	SE
Slit Lamp Examination	x	SE	SE	SE	SE	SE	SE	SE	SE	SE	SE	SE	SE	SE	SE	SE	SE
LOCS III Lens Grading F	x	SE	SE	SE	SE	SE	SE	SE	SE	SE	SE	SE	SE	SE	SE	SE	SE
Dilated Binocular Indirect Ophthalmoscopy	x	SE	SE	SE	SE	SE	SE	SE	SE	SE	SE	SE	SE	SE	SE	SE	SE
SD-OCT G	x				SE				SE						SE		x
Fundus Autofluorescence Photographs (FAF) G	x				x				x						x		x
Infrared Reflectance (IR) G	x				x				x						x		x
Digital Color Fundus Photographs (DCFP)	x																x
Fundus Fluorescein Angiograms (FFA)	x																x
Study Eye Determination	x																
Randomization		X															
APL-2 administration or Sham Injection		X		x	x	x	x	x	x	x	x	x	x	x	x		
Post-Injection Assessment H		X		x	x	x	x	x	x	x	x	x	x	x	x		
Concomitant Medication / Adverse Events		X	x	x	x	x	x	x	x	x	x	x	x	x	x	x	x

SE= Study eye only

Statistical Analysis Plan

Every-Other-Month (EOM) Groups Visit Schedule												
	Visit # Day Deviation Allowed (+ or - days) Month	Screening	Treatment							FU	Termin.	
		1	2	3	4	5	6	7	8	9	10	11
		-14	0	7	60	120	180	240	300	360	450	540
		5	0	1	6	6	6	6	6	6	14	14
		-0.5	0	0	2	4	6	8	10	12	15	18
Informed Consent / Assign Screening Number	X											
Demographic Data	X											
Inclusion/Exclusion Criteria A	X	x										
Medical/Ocular history	X											
Blood Draw – Safety Labs B	X			x		x			x		x	
Urine Sample Collection	X			x		x			x		x	
Blood Draw - PK and Anti-APL-2 Ab	X		x	x	x	x	x	x	x	x	x	
Blood Draw – Genotyping (if applicable) C				x								
Vital Signs D	X	x	x	x	x	x	x	x	x	x	x	
Urine Pregnancy Test E				x	x	x	x	x	x	x	x	
BCVA	X	SE	SE	SE	SE	SE	SE	SE	SE	x	SE	
LL-BCVA	X	SE	SE	SE	SE	SE	SE	SE	SE	x	SE	
IOP Measurement	X	SE	SE	SE	SE	SE	SE	SE	SE	SE	SE	
Slit Lamp Examination	X	SE	SE	SE	SE	SE	SE	SE	SE	SE	SE	
LOCS III Lens Grading F	X	SE	SE	SE	SE	SE	SE	SE	SE	SE	SE	
Dilated Binocular Indirect Ophthalmoscopy	X	SE	SE	SE	SE	SE	SE	SE	SE	SE	SE	
SD-OCT G	X			SE		SE			SE		x	
Fundus Autofluorescence Photographs (FAF) G	X			x		x			x		x	
Infrared Reflectance (IR) G	X			x		x			x		x	
Digital Color Fundus Photographs (DCFP)	X										x	
Fundus Fluorescein Angiograms (FFA)	X										x	
Study Eye Determination	X											
Randomization		x										
APL-2 administration or Sham injection		x		x	x	x	x	x	x			
Post-Injection Assessment H		x		x	x	x	x	x	x			
Concomitant Medication / Adverse Events		x	x	x	x	x	x	x	x	x	x	

SE= Study eye only

## Statistical Analysis Plan

---

- A. On visit 2, review inclusion/exclusion and confirm eligibility by the Central Reading Center (CRC).
- B. Includes HCG for WOCBP and FSH/LH blood for postmenopausal females at screening.
- C. Genotyping will only be performed at selected sites.
- D. On injection visits, vital signs will be measured within approximately 1 hour prior to dosing and within 30 minutes after dosing.
- E. Only WOCBP
- F. If a lens finding is noted during the slit-lamp examination, at any visit, then the finding should be further characterized with LOCS III. All subsequent visits for that patient should include LOCS III.
- G. On injection visits, SD-OCT, FAF and IR should be performed before APL-2 (or Sham) administration. IR will only be done at selected clinical sites with Heidelberg Spectralis® system.
- H. Initial assessment must be done within 15 minutes after dosing. Additional assessments should be done every approximately 30 minutes, if needed.

Note: The study schedule refers to the first day of dosing as Day 0 (Visit 2). For reporting purposes CDISC standards will be used and therefore it is necessary to refer to the first day of dosing as Day 1. Consequently, throughout the SAP text Day 1 is referred to as the first day of dosing, however the study schedule table is taken directly from the protocol and has not been changed.

## Statistical Analysis Plan

---

### 4. ENDPOINTS

#### 4.1. PRIMARY EFFICACY ENDPOINT

The primary endpoint is the annual growth rate of GA area in the study eye as measured by the mean change in square root area of GA lesion from baseline to Month 12 based on the Fundus Autofluorescence Photographs (FAF). Baseline will be taken as the last available non-missing assessment prior to first study drug administration, this should be the screening assessment for the primary endpoint.

A secondary endpoint will investigate the untransformed value collected i.e. mean change in area of GA lesion from baseline to Month 12 based on the FAF.

Upon reviewing the 12-month results, different growth rates in the GA lesion were observed across visit to visit. Therefore, the change in GA lesion from Month 6 to Months 12 and 18, and the change from Month 12 to Month 18 will be evaluated as exploratory endpoints. The analyses will be performed for both square root transformed and untransformed measurements of the GA lesion.

#### 4.2. SECONDARY AND EXPLORATORY EFFICACY ENDPOINTS

##### 4.2.1. Best-Corrected Visual Acuity (BCVA)

BCVA is performed following refraction by a certified VA examiner and is done prior to any examination requiring administration of eye drops to dilate the eye or any examination requiring contact with the eye. Larger values indicate better visual acuity. BCVA is the sum of BCVA1 (correct identifications at 1 meter) and BCVA4 (correct identifications at 4 meters). If BCVA1 is not collected because visual acuity has been identified as 20/200 or better at the 4-meter test, then a value of 30 will be used in the calculation of BCVA.

The endpoint is change from baseline in BCVA. Baseline will be taken as the last available non-missing assessment prior to first study drug administration. The change from baseline will also be categorized as follows:

- $\geq 15$  letters improvement from baseline
- $\geq 10$  letters and  $< 15$  letters improvement from baseline
- $\geq 5$  letters and  $< 10$  letters improvement from baseline
- Minimal change from baseline; defined as -4 to 4 letters
- $\geq 5$  letters and  $< 10$  letters worsening from baseline
- $\geq 10$  letters and  $< 15$  letters worsening from baseline
- $\geq 15$  letters worsening from baseline

The Snellen equivalent value is also collected as part of the BCVA assessment. The Snellen equivalent categorical response at each visit will be investigated. In addition, the Snellen value will

## Statistical Analysis Plan

---

be transformed to  $\log_{10}$  of the reciprocal of the Snellen value, this is more commonly known as  $\log_{10}$  of the minimal angle of resolution value (logMAR). The converted logMAR scores will be rounded to one decimal. For a Snellen value of 20/20 logMAR is 0 and as vision worsens logMAR increases and as vision improves logMAR decreases. A change of 0.1 on the logMAR scale represents a change of 1 line. The change from baseline in logMAR will be investigated.

### **4.2.2. Macular Neovascularization (MNV)**

The incidence of MNV in the study eye will be investigated. A clinical review of all ocular adverse events will be performed prior to database lock to identify all cases of MNV.

### **4.2.3. Low Luminance Best-Corrected Visual Acuity (LL-BCVA)**

LL-BCVA is performed by a certified VA examiner and is done prior to any examination requiring administration of eye drops to dilate the eye or any examination requiring contact with the eye. Larger values indicate better visual acuity. LL-BCVA is the sum of LL-BCVA1 (correct identifications at 1 meter) and LL-BCVA4 (correct identifications at 4 meters). If LL-BCVA1 is not collected because the low luminance visual acuity has been identified as 20/200 or better at the 4-meter test, then a value of 30 will be used in the calculation of LL-BCVA.

The endpoint is change from baseline in LL-BCVA. Baseline will be taken as the last available non-missing assessment prior to first study drug administration. The change from baseline will also be categorized as follows:

- $\geq 15$  letters improvement from baseline
- $\geq 10$  letters and  $< 15$  letters improvement from baseline
- $\geq 5$  letters and  $< 10$  letters improvement from baseline
- Minimal change from baseline; defined as  $-4$  to  $4$  letters
- $\geq 5$  letters and  $< 10$  letters worsening from baseline
- $\geq 10$  letters and  $< 15$  letters worsening from baseline
- $\geq 15$  letters worsening from baseline

The Snellen equivalent value is also collected as part of the LL-BCVA assessment. The Snellen equivalent categorical response at each visit will be investigated. In addition, the Snellen value will be transformed to logMAR (as described in Section 4.2.1). The change from baseline in logMAR will be investigated.

### **4.2.4. Low Luminance Visual Acuity (LL-VA) Deficit**

The LL-VA deficit is calculated as BCVA minus LL-BCVA. The endpoint of interest is change from baseline in LL-VA deficit. Baseline will be taken as the last available non-missing assessment prior to first study drug administration. Baseline LL-VA deficit should be derived from BCVA and LL-BCVA

## Statistical Analysis Plan

---

at the same time point for each subject; otherwise baseline LL-VA deficit will be set to missing.

### **4.2.5. Foveal Encroachment (Distance of GA Lesion from Fovea)**

Foveal encroachment over time in the study eye, as measured by FAF, will be assessed by change from baseline in distance of GA lesion from fovea. Baseline will be taken as the last available non-missing assessment prior to first study drug administration.

### **4.2.6. Drusen Size**

Drusen is assessed in both eyes by color photography at screening and end of study or early termination. Baseline will be taken as the last available non-missing assessment prior to first study drug administration. The endpoints are:

- Study eye drusen size (none, small, intermediate or large). The maximum size recorded will be used. So for example if both intermediate and large drusen are recorded then the size will be large. The size will be assigned as small if there are drusen present but none are intermediate or large.
- The number of intermediate or large drusen recorded in the study eye (0-5, 6-10, 11-20 or >20).

### **4.2.7. GA Lesion Size Measured by SD-OCT**

In this study, Spectral Domain Optical Coherence Tomography (SD-OCT) is measured by one of two machines (Ziess Cirrus or Heidelberg Spectralis). The same machine is used for a subject throughout the study. *Note: approximately 80% of subjects have been assessed using the Spectralis machine.*

Depending on data availability, GA lesion size per SD-OCT will be investigated for those subjects who have SD-OCT assessed with the Cirrus machine. The endpoint is change from baseline in square root area for GA lesion in the study eye as measured by SD-OCT. Baseline will be taken as the last available non-missing assessment prior to first study drug administration.

### **4.2.8. Genetic Polymorphisms**

Genetic marker analysis will be performed on blood samples collected at Month 2 for all subjects at selected sites where genetic testing is allowed. The prioritized genes, C3, CFI, CFH, CFB, C2, ARMS2/HTRA1, will be explored to assess whether they are prognostic/predictive factors of the growth in GA area and the APL-2 treatment. For the prioritized genes the following SNPs, that have been highly associated with AMD, will be investigated:

- CFH: rs1061170, rs1410996, rs10737680, rs1048663
- CFB: rs438999, rs541862, rs4151667, rs641153
- C2: rs9332739

## Statistical Analysis Plan

---

- C2/CFB: rs429608
- CFI: rs17440077, rs4698775, rs10033900
- ARMS2/HTRA1: rs10490924
- C3: rs2230199

Additional genes that are not part of the current scope of work may be analysed and summarized in a separate genetic report.

### **4.3. SAFETY ENDPOINTS**

#### **4.3.1. Adverse Events**

The primary safety endpoints for the study are the number and severity of treatment emergent adverse events (TEAEs) and adverse events of special interest (AESI). AESI will be identified on the eCRF at the time of reporting and include:

- Endophthalmitis
- 4+ ocular inflammation
- 2-3+ ocular inflammation that fails to decrease to 1+ or less within 30 days of the onset of the event
- Sustained (> 5 minutes) loss of light perception after APL-2 (or Sham) injection
- Sustained elevation of IOP (30 mmHg) at/past 90 minutes post-injection
- Any elevation of IOP requiring surgical intervention (i.e. paracentesis)
- New vitreous hemorrhage of > 2+ severity that does not resolve within 14 days of the onset of the event
- Progression to exudative (wet) AMD in the study eye or fellow eye requiring surgical intervention (Note: Intravitreal administration of anti-VEGF agents are not considered surgical interventions.)

A clinical review of all ocular AEs will be performed prior to database lock to ensure all AESI have been identified.

#### **4.3.2. Intraocular pressure (IOP)**

Intraocular pressure (IOP) will be measured using either Tonopen, iCare or Goldmann applanation tonometer. The same method will be used for all measurements in the same subject throughout the study. IOP is collected for the study eye pre and post injection at each study visit.

A safety endpoint for IOP is change from baseline in study eye IOP over time. Baseline will be taken as the last available non-missing assessment prior to first study drug administration.

The acute change in IOP after each injection (i.e., change from pre-injection to post-injection value) will also be analysed as another endpoint for IOP. Missing pre-injection IOP values will be imputed

## Statistical Analysis Plan

---

with the last available pre-injection IOP value at previous visits. Missing post-injection values will not be imputed.

Values  $\geq 30$  mmHg will also be identified. Missing IOP values will not be imputed for this indicator endpoint.

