8.3.4 Injection Visits – Monthly or EOM until month 12 -

Monthly Groups: Days 30, 60, 90, 120, 150, 180, 210, 240, 270, 300, 330 and 360 - Visits 4, 5, 6, 7, 8, 9, 10, 11, 12, 13, 14 and 15, respectively.

EOM Groups: Days 60, 120, 180, 240, 300 and 360 – Visits 4, 5, 6, 7, 8 and 9 respectively.

Unless specified, all ophthalmic procedures (including imaging) are to be performed on the **study eye only**. The following procedures will be performed at all injection visits:

1. Obtain information on any changes in medical health and/or the use of concomitant medications.
2. Collect vital signs pre- and post-dose. Vital signs will be measured within approximately 1 hour prior to dosing for the pre-dose time point. Post-dose vital signs readings will be performed within 30 minutes after dosing.
3. Collect blood for PK analysis.
4. Perform urine pregnancy test before APL-2 injection. **-WOCBP only-**
5. Perform BCVA. **-Both eyes on Day 360 only-**
6. Perform LL-BCVA. **-Both eyes on Day 360 only-**
7. Perform a complete ophthalmic exam including slit-lamp exam of the cornea, iris, anterior chamber, lens (LOCS III if any opacity on the lens noted) and aqueous reaction (cells and flare), dilated fundus exam of the vitreous and retina and IOP measurement.
8. Perform the IVT injection of APL-2 (or Sham injection) as described in the MOP.
9. Monitor the study eye within 15 minutes post-injection as outlined in [Section 9.8](#) and in the MOP.
10. Monitor for adverse events.

The following procedures will be performed only at specific visits, as noted:

1. Collect blood and urine for laboratory analysis and forward the samples to the central laboratory. - **Only on Days 60, 180 and 360 for all groups -**
2. Collect blood for genetic marker analysis (if applicable, see [Section 9.3](#)) and forward the samples to the central laboratory. - **Only on Days 60 for all groups -**
3. Perform SD-OCT imaging and forward the images to the CRC. - **Only on Days 60, 180 and 360 for all groups -**
4. Perform FAF imaging **of both eyes** and forward the images to the CRC. - **Only on Days 60, 180 and 360 for all groups -**
5. Perform IR imaging (if applicable) **of both eyes** and forward the images to the CRC. - **Only on Days 60, 180 and 360 for all groups -**

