### **11.2. INTRA OCULAR PRESSURE (IOP)**

The observed and change from baseline values in IOP over time will be summarized by treatment group and protocol specified time points for the safety population. Summaries will present the descriptive statistics for baseline and change from baseline data. The acute change in IOP after each injection (i.e., change from pre-injection to post-injection value) will also be summarized at each protocol specified time point.

The number of subjects with IOP  $\geq 30$  mmHg post injection will be summarized by treatment group, visit and over the whole study.

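### A missing pre-injection IOP is filled from an earlier visit, so the acute IOP change for that injection also contains between-visit change; the effect on the summary is minor

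*SAP*

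**What the plan says.** SAP 4.3.2 makes the injection-related pressure change an endpoint of its own: "The acute change in IOP after each injection (i.e., change from pre-injection to post-injection value) will also be analysed as another endpoint for IOP". The same section then sets three missing-data rules:

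- Pre-injection: "Missing pre-injection IOP values will be imputed" "with the last available pre-injection IOP value at previous visits". No maximum look-back is stated.
- Post-injection: "Missing post-injection values will not be imputed".
- Indicator of IOP at or above 30 mmHg: "Missing IOP values will not be imputed for this indicator endpoint".

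SAP 11.2 gives the planned output: "The acute change in IOP after each injection (i.e., change from pre-injection to post-injection value) will also be summarized", by time point. It provides no flag for imputed records and no summary restricted to observed pairs. SAP 6.2 says that listings always show the original data.

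Protocol 8.3.4 fixes the spacing of the injections after Day 0: "Monthly Groups: Days 30, 60, 90, 120, 150, 180, 210, 240, 270, 300, 330 and 360" and "EOM Groups: Days 60, 120, 180, 240, 300 and 360".

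**The concern.** The endpoint is meant to isolate what an injection does to pressure on the day. Protocol 9.8 puts the first post-injection check within 15 minutes, so an observed pair spans a short interval within one visit. Once the pre-injection value comes from an earlier visit, the difference spans weeks and no longer measures the endpoint as defined.

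The direction of the error depends on what happened in between. If resting pressure has risen, the spike is overstated. If pressure-lowering treatment has been started, it is understated. Protocol 4.3 lists a passing pressure rise among the injection risks, and the Synopsis makes IOP increase a secondary safety endpoint, so the table should describe the injection effect cleanly.

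The rule is also out of step with the SAP's own practice. For baseline low-luminance deficit, another difference of two readings, SAP 4.2.4 requires both components from the same time point and otherwise sets the value to missing. SAP 11.5 flags imputed LOCS III baselines in the listing. No reason is given for handling pre-injection IOP differently.

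**Working it through.** The plan states no sample size, power or expected value for the acute IOP change, so there is no figure to reproduce. The check covers the look-back, the algebra and the possible size.

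**1. Look-back**

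Inputs: the injection days in Protocol 8.3.4, Day 0, and the windows in the Protocol section 2 flow charts (±6 days at injection visits, none at Day 0).

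- Monthly: nominal gap 30 days. With windows at both ends, 30 − 12 = 18 to 30 + 12 = 42 days. Counting from Day 0, 24 to 36 days.
- EOM: nominal gap 60 days. With windows at both ends, 60 − 12 = 48 to 60 + 12 = 72 days. Counting from Day 0, 54 to 66 days.
- Each further missing pre-injection value adds another nominal 30 or 60 days.
- A missing Day 0 value could draw on screening, nominally 14 days before.
- IOP is also read at Day 7, when no injection is given. The SAP does not say whether that reading counts as a pre-injection value. If it does, the nominal gap to the next injection visit is 30 − 7 = 23 days (monthly) or 60 − 7 = 53 days (EOM).

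**2. What an imputed record contains**

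Observed pair: D(t) = post(t) − pre(t).

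Imputed record: D*(t) = post(t) − pre(t−k) = D(t) + [pre(t) − pre(t−k)].

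The bracket is the between-visit change in pre-injection IOP, and it enters in full.

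**3. Bias in the arm mean**

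Bias = f × mean drift, where f is the share of imputed records. The documents give neither quantity, so both are assumed (results in mmHg):

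| f | drift 0.5 | drift 1 | drift 2 | drift 3 |
|---|---|---|---|---|
| 1% | 0.005 | 0.01 | 0.02 | 0.03 |
| 5% | 0.025 | 0.05 | 0.10 | 0.15 |
| 10% | 0.05 | 0.10 | 0.20 | 0.30 |

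If drift averages zero, the bias is zero.

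**4. Added noise**

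Assume a true acute-change SD s of 4-6 mmHg and a between-visit difference with SD w of 2-4 mmHg, independent of the acute change.

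- One imputed record: √(s² + w²), from √(16 + 4) = 4.47 to √(36 + 16) = 7.21 mmHg.
- Whole arm: √(s² + f·w²). The largest relative increase at f = 10% is at s = 4, w = 4: √(16 + 1.6) = 4.20, against 4.00, or about 5%.

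**5. After the fix**

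With observed same-visit pairs only, the bracket in step 2 disappears by construction. The number of records falls by the number that lack a pre-injection value.

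**The case against.** The other side has a good case on consequence. SAP 4.3.2 says IOP is collected before and after injection at each visit, so a missing pre-injection value is an exception to the schedule; only records that also have a post-injection value are touched. The acute change is summarised descriptively, without a test. The outputs that matter most for safety do not use it: the indicator at 30 mmHg is explicitly not imputed, the IOP adverse events of special interest in SAP 4.3.1 are not built on this difference, and on-site monitoring under Protocol 9.8 uses measured pressures. Original data stay in the listings, so observed pairs can be recovered. Deleting the rule also drops some observed post-injection readings from this one table.

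All of that stands, and it limits the size. It does not make the imputed value a measurement of the stated endpoint. If few values are missing, imputation gains almost nothing; if many are, it distorts the table.

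Three stronger readings are tempting but unsupported:

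- *Every imputed record reaches back at least 30 or 60 days.* Those gaps are nominal; the windows and the Day 0 case allow shorter ones.
- *The summary is off by several mmHg.* If single-visit readings vary independently with an assumed SD of 2, 3 or 4 mmHg, the substitution error is √2 times that: 2.8, 4.2 or 5.7 mmHg. This is the error SD of one imputed record, not of an arm mean. Under the same independence assumption it is identical at 30 and 60 days, so it says nothing about the longer EOM gap.
- *The longer EOM look-back biases APL-2 against sham.* Each APL-2 schedule has a sham arm with the same look-back, SAP 6.1 shows the two sham arms separately, and each pooled group combines the schedules 1:1 by randomization. A common look-back does not guarantee equal drift, but the documents give no evidence of a difference.

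**Conclusion.** The point holds, as a minor one. The rule in SAP 4.3.2 gives a value that differs from the endpoint it is meant to supply, and SAP 11.2 does not separate those values from observed ones. That much follows from the text alone.

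The size rests on assumptions, because the documents give no missing rate and no IOP variability. With 1-10% of records imputed and a mean drift of 0.5-3 mmHg, the arm mean moves by about 0.005-0.30 mmHg. Bias needs a systematic shift in pre-injection pressure, and the documents do not show one. A single imputed record still carries its full drift and could set the minimum or maximum that SAP 6.1 asks to be reported.

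A reader might infer that IOP safety monitoring as a whole is compromised. It is not: the defect is confined to one descriptive summary.

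**What to change.** Delete the pre-injection imputation sentence in SAP 4.3.2 and state that the acute change is computed only when both readings were observed at the same injection visit. In SAP 11.2, show the number of such pairs beside the number of injections given, by arm and visit. If a carried-forward version is wanted, keep it as a sensitivity summary with the imputed records flagged.

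If the Month 12 tables already exist, the observed-pairs table can go into the CSR addendum that SAP 2 and SAP 12 already plan, with the change documented.

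The cost is one sentence and, if missing readings are as rare as the schedule suggests, a few records fewer in this descriptive summary.
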